Intended content. The content of the TYRO Couples curriculum focuses on how to understand your partner's perspective, how to avoid destructive conflict, and how to communicate effectively that is applicable to both the workplace and personal relationships. TYRO Couples prepares individuals for healthy relationships, strengthens existing relationships, enhances parenting skills, and creates a harmonious workplace and family dynamic. TYRO Couples offers a holistic approach to building healthier, happier families and leaders in their homes, communities, and workplaces. TYRO Couples teaches self-efficacy, whether that is in personal relationships or the ability to job search, secure employment, build job skills, or maintain employment relationships. Participants embark on a transformative journey towards deeper connection, effective communication, thriving careers, and empowered parenting.

The content, whether delivered in-person or on-demand, is designed to help individuals learn the skills to have healthy relationships, regardless of their current relationship status or desire to be in a relationship. Individuals learn to identify cycles of unhealthy relationship behaviors and how to replace those behaviors with healthy habits. Self-awareness, self-regulation, dream-pursuit, healthy communication, conflict resolution skills, and relational investment metrics are taught to help inspire participants to desire a healthy relationship regardless of marital status. Most participants have been in previous, unhealthy relationships that ended and a small percentage are in a current relationship. As of grant year four and taking into consideration everyone who enrolled into the study and completed an Applicant Characteristics Survey (ACS), over 50% of participants who responded to the item stated that they did not have a current partner. In addition, about 29% reported being romantically involved or in a committed relationship, and 17% reported being involved in an on-again off-again relationship (among those who responded to the survey item). Final numbers for the analytic sample of RCT participants will be included in the final report. By teaching participants self-improvement guided by self-awareness and self-regulation, they learn what it takes to develop a strong, thriving, healthy and permanent relationship.

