Raw data sets will be cleaned and prepared for analysis using the R Studio statistical software. nFORM survey responses and participant information (e.g., study group assignment) will be downloaded using the Data Export feature of nFORM, and local evaluation survey responses will be exported from Qualtrics as Excel files. All exports will be imported into R and cleaned separately before data sets are merged into a final, wide format file for analyses using nFORM Client ID as the unique identifier for matching observations. Planned procedures for data cleaning and handling missing data are detailed below.

Inconsistent or seemingly inaccurate data

To address participant feedback about the relevance of some local evaluation survey items, evaluators added skip logic to local evaluation surveys in October 2023 for relationship attitudes and behaviors (which are used in a secondary research question because they are not applicable to the entire sample).

Measures for primary research questions only use items that are applicable to the entire study population. However, secondary exploratory research questions include items that are not applicable to the entire study population as not all study participants report being in a committed relationship.

See Figure A.4. for a full breakdown of survey items, including which had skip logic added.

In addition, preliminary analyses showed relationship questions had 25-28% of missing responses. After the skip logic was added, participants who reported not being in a committed relationship were permitted to skip questions about relationship behaviors, and participants who reported not being currently employed were permitted to skip some questions about employment behaviors. Some participants may have responded to these questions at baseline but not been shown the same questions at follow-up due to the added skip logic. For example, a participant might have been in a relationship at the time of the baseline survey completion, but not at the time of the follow-up survey completion.

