Each of the outcomes for the primary research questions for this study are constructed averages using multiple, related survey items. Sufficiently high item nonresponse among items used to construct outcome measures will lead to sample attrition for that outcome. The evaluation team plans to use an 80% threshold as the cutoff for constructed measures; respondents who answer less than 80% of survey items associated with a constructed measure will be dropped from the analysis for that outcome. The constructed average for each participant who has answered at least 80% of associated survey items will be calculated by dividing the sum of their survey answers by the number of items they answered. For example, if a participant answers 8 out of 10 survey items associated with a construct, their average for that outcome measure will be the sum of their 8 answers divided by 8. The evaluation team does not plan to use imputation for multi-item constructed outcomes with 20 percent or fewer missing items. A sensitivity analysis will be conducted to see if and how results would change with a 70% threshold cutoff instead of an 80% cutoff.

2. Attrition and analytic sample

The analytic sample for each outcome construct identified in Table 2 will consist of study participants who have a non-missing value at baseline and follow-up time points for that construct (complete case). The size of the analytic sample may vary by outcome measure based on the prevalence of item non-response missing data at the baseline and follow-up surveys for the items used to create those composite measures. For attitudinal outcomes related to economic stability, and finances, all respondents with complete case data will be included in the analytic sample. For relationship behavior outcomes, participants will be included in the analytic sample if they report being in a committed relationship at the time the survey was administered (i.e., do not choose 'no' for the skip logic question 'Are you currently in a committed romantic relationship?'). Because this skip logic was added to the local evaluation surveys belatedly (in October 2023), this condition will only apply to those respondents who took a survey with this skip logic. For those respondents who took a survey before this relationship skip logic was added, all participants who have complete case data will be included in the analytic sample in response to the secondary research question.

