Analyses will be conducted using the R Studio statistical software package. The basic model for this impact evaluation will include a dummy variable for intervention group assignment, equal to 1 if a participant was randomly assigned to receive the curriculum on-demand via tablet, and a participant's score at baseline as the main predictors of each outcome measure at follow-up. To enhance the precision of the impact estimates, we plan to include several other covariates in our models. For all outcome analyses, we will control for participant age, gender, and race, as well as the timing of a participant's follow-up survey (number of days between program enrollment and follow-up survey completion). We will also consider including a facility indicator to denote which site the participant received services at. Additionally, we will include any demographic variables that were shown to be significantly different between study groups during baseline equivalency analysis. For the healthy relationship attitudes outcome, we also plan to include relationship status at baseline as a covariate. This will only be available if a participant reports being in a relationship at baseline and at follow-up.

Table 6. Covariates included in impact analyses

Covariate	Description of the covariate
Age	Age (in years) as of the baseline data collection, as reported on the ACS
Gender	Self-reported gender identification as of the baseline data collection, as reported on the ACS
Race	Self-reported racial identification as of the baseline data collection, as reported on the ACS

Covariate	Description of the covariate
Timing of follow-up survey	Number of days between program enrollment date and date of follow-up survey completion to control for variation in survey timing
Relationship status (relationship attitude and behavior outcomes only)	Relationship status (1 = in a committed relationship, 0 = not in a committed relationship) as of the baseline data collection, as reported on the ACS

4. Sensitivity analyses for primary research questions

We plan to conduct several sensitivity analyses to test the robustness of our results. First, and as mentioned earlier in the plan, we will conduct a sensitivity analysis to see if and how our outcome construct measures change if we use 70% as a threshold for non-missing items instead of 80% as a threshold.

[figure not shown]

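### The follow-up condition on the baseline relationship-status covariate conflicts with Table 6 and with the timing of the attitudes outcome, and selection on later relationship status goes unacknowledged

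*Combined protocol and SAP*

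**What the plan says.** Section D.3 (Modeling approach) states: "For the healthy relationship attitudes outcome, we also plan to include relationship status at baseline as a covariate". The next sentence limits it: "This will only be available if a participant reports being in a relationship at baseline and at follow-up".

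Table 6, in the same section, describes the variable as "Relationship status (1 = in a committed relationship, 0 = not in a committed relationship) as of the baseline data collection, as reported on the ACS". Its row label is "Relationship status (relationship attitude and behavior outcomes only", so it serves both relationship outcomes, whereas the text names attitudes only.

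The surrounding rules matter as well:

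- **Timing.** The second secondary research question and Table 2 place relationship attitudes at the post-survey, after program completion. Section C.2 puts that survey six weeks after enrollment. Relationship behaviors are measured at six months.
- **Who answers the ACS item.** Section B.2 reports that "over 50% of participants who responded to the item stated that they did not have a current partner", with about 29% involved or committed and 17% on-again off-again.
- **Sample rule.** For relationship behaviors, Section D.2 says "participants will be included in the analytic sample if they report being in a committed relationship at the time the survey was administered". Respondents surveyed before the October 2023 skip logic are exempt and enter if their data are complete.
- **Change of status.** Section D.1 accepts that "a participant might have been in a relationship at the time of the baseline survey completion, but not at the time of the follow-up" survey.
- **Missing data.** Section D.2 requires the construct at both time points and rules out imputation of baseline or outcome values.

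**The concern.** A value recorded on the ACS at baseline exists whatever happens later, so a covariate that is both a baseline ACS value and available only to people still partnered at follow-up is defined in two incompatible ways. An analyst who follows the D.3 sentence under complete-case analysis keeps only people in a relationship at both times. With Table 6's coding, nearly all of them carry the value 1, and the planned adjustment does little or nothing.

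The same step would make later relationship status a condition of entry to the attitudes model. That status arises after assignment. If one delivery format were followed by more break-ups than the other, and relationships that ended would have scored lower, the arm losing more of them would look better among those who remain. No planned analysis examines this; the sensitivity analyses in Section D.4 are for the primary questions.

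**Working it through.** The plan states no figure on this point, so there is none to reproduce.

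**1. The two definitions side by side**

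| Feature | D.3 text | Table 6 |
|---|---|---|
| Source | Baseline status | Baseline ACS |
| Available to | Those in a relationship at baseline and follow-up | No restriction stated |
| Outcomes | Attitudes | Attitudes and behaviors |

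The attitudes outcome itself is taken at the post-survey, which neither time point in the D.3 condition names.

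**2. Does the covariate vary?** A regression design matrix was built with 200 simulated rows and five columns: intercept, arm, two continuous covariates and status.

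- Status all 1: rank 4 of 5. The term is aliased with the intercept and drops out.
- 5% coded 0: rank 5 of 5. The term is estimable, but its variance is only 0.05 × 0.95 = 0.0475, against a maximum of 0.25 for a 1/0 variable.
- 37% coded 0 (17/46, if on-again off-again is coded 0 and all such people are kept): rank 5 of 5, variance 0.37 × 0.63 = 0.233.

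**3. People lost if follow-up means the six-month survey.** Figure A.3, from the July 2024 data pull, shows 64 of 206 and 52 of 190 eligible participants with a completed follow-up.

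- Completed: 64 + 52 = 116. Eligible: 206 + 190 = 396. 116/396 = 29%.
- The other 280 (71%) had no six-month report at that date. Any of them with valid post-survey attitudes would be lost.

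This is an interim snapshot of all participants, partnered or not, and completion may rise.

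**4. Size of a selection bias.** Let *g* be the gap in SD between relationships that continue and those that end, and let *p1* and *p2* be the shares ending in each arm. Suppose there is no true effect, so the full-arm means are equal. The mean among continuers is then *g* × (share ended), and

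bias = *g* × (*p2* − *p1*), in favor of the arm with more break-ups.

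- *g* = 0.5, 20% versus 30%: 0.5 × 0.10 = 0.05 SD.
- *g* = 1.0, 20% versus 30%: 1.0 × 0.10 = 0.10 SD.

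A simulation with no true effect, and an assumed correlation of 0.3 to 0.5 between the outcome and a latent tendency to stay partnered, gives:

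| Retention, on-demand vs in-person | Bias against on-demand (SD) |
|---|---|
| 70% vs 70% | 0 |
| 75% vs 70% | 0.02 to 0.04 |
| 80% vs 70% | 0.04 to 0.07 |
| 75% vs 60% | 0.07 to 0.11 |

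Together the two methods give about 0.04 to 0.10 SD for a 10-point difference. Every retention rate, gap and correlation here is an assumption; the documents give none.

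**5. Scale.** If the ACS shares apply to the target of 768:

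- 29% gives 0.29 × 768 ≈ 223, about 111 per arm. The minimum detectable effect is (1.96 + 0.84) × √(2/111) ≈ 0.38 SD.
- 46% (29% + 17%) gives about 353, and about 0.30 SD.

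Two-sided alpha of 0.05 and 80% power are assumed, since the plan states neither.

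**The case against.** The strongest reply is that much of this depends on one loosely worded sentence.

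- **The covariate is not certainly constant.** A reader might infer that it must be. The documents do not settle this. Section D.2 admits complete-case respondents surveyed before the skip logic whatever their status, Section D.1 keeps some answers given against the skip instructions, and nothing says whether on-again off-again is coded 1 or 0. Any of these could supply zeros. This stands, so the claim is limited to constant or nearly so under the literal rule.
- **The sentence is not the main source of selection.** A reader might infer that the covariate rule creates the selection and that deleting it removes the problem. It does not. The relationship questions are limited to people reporting a relationship, the skip logic removes the others, and D.2 writes the restriction into the behavior sample. This also stands.
- **Shared content does not imply a difference in break-ups.** It is tempting to argue that a relationship curriculum changes who stays partnered and so biases the contrast. Both arms receive the same content, so delivery format itself would have to change retention. No document says that it does. Adjustment for baseline score would also remove part of any bias, as far as that score predicts staying together.
- **The wording is ambiguous.** The availability sentence may refer to outcome data rather than the covariate, and follow-up may loosely mean whichever survey supplies the outcome. In that case the loss in step 3 would not arise. The conflict in wording would remain, and the sample would still consist largely of people partnered at both times.
- **The outcomes are exploratory.** The plan calls them so and says any assessment of them would be underpowered. That limits the severity.

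**Conclusion.** The conflict is real. The D.3 sentence cannot be reconciled with Table 6, and a follow-up condition does not fit an outcome taken at the post-survey. Followed literally under complete-case analysis, it leaves a covariate that adjusts for little, conditions the attitudes model on a post-assignment state, and may discard people with valid post-survey data.

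Selection on later relationship status comes mainly from the skip logic and the D.2 rule, for respondents surveyed after the October 2023 change. Its effect on the arm contrast is unknown: zero if retention is equal across arms, and about 0.04 to 0.10 SD under an assumed 10-point difference. The documents do not show that such a bias exists. That range is also small beside the roughly 0.30 to 0.38 SD detectable in these subgroups under the stated assumptions.

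The primary outcomes, employment and financial attitudes, are unaffected. Severity is minor.

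**What to change.** 1. Delete the follow-up condition from Section D.3.
2. Use the baseline ACS value for every participant in both relationship models, so that the text and Table 6 agree. State how on-again off-again is coded, and drop the term if it does not vary in the analysed sample. Replacing it with a committed versus on-again off-again contrast is not a safe alternative: the skip question asks about a committed relationship, so the second group may largely be screened out.
3. Report by arm the share of those partnered at baseline who still report a relationship at Wave 2 and at Wave 3.
4. Label the relationship-scale comparisons as conditional on being partnered when surveyed, not as the effect in all randomised participants. Steps 3 and 4 are needed because step 1 alone leaves the D.2 selection in place.

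The cost is a few lines of plan text and one table built from items already collected. No new data are needed.

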Outcome measures in this study were created for this evaluation and are not based on already-validated scales. Using the local evaluation baseline survey, we will generate a correlation matrix between items in a given construct to ensure that theoretically related items are also empirically related in our data set. Items that are not strongly correlated with other items in a construct will be removed as necessary. Factor analysis will be used to ensure that all construct items hang together (using an alpha of 0.60 or higher as the threshold). We will then create a composite measure by taking an average of the scores on each non-missing item in the construct. For composite measures, a change score will be calculated between a participant's pre-program composite score and six-month-post-enrollment follow-up composite score. If construct items do not meet the 0.60 threshold, that outcome will be removed. An alpha value of 0.60 is the minimally acceptable value that will be used for scale construction.

We will create a composite score by taking the average of multiple individual items. For these composite measures, our plan is to use 20% as a threshold for allowable missing items. This plan is contingent on the final distribution of missing data in our dataset. With a 20% threshold, if a respondent is missing more than 1 item used for creating the employment construct or more than 2 items for creating the financial construct, the respondent will be assigned a missing value for that construct. We will not impute truly missing values for outcomes. To create a construct score, the average will be divided by the number of non-missing values in the construct.

Table 1. Description of outcome measures used to answer impact analysis primary research questions

Research question #	Outcome name	Description of the outcome measure and its properties	Source of the measure	Timing of measure
1	Employment Attitudes	
The outcome measure is a scale (value range of 1=strongly disagree to 5=strongly agree) calculated as the average of eight survey items related to employment attitudes.
 
Sample item: I have the skills I need to get a decent job.
	Local evaluation follow-up-survey	Six months after program enrollment

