Because outcome measures for this impact study are constructed from survey items from both nFORM and the local evaluation surveys, survey nonresponse on either the nFORM baseline survey, local evaluation baseline survey, nFORM exit survey, local evaluation post survey, or local evaluation follow-up survey can lead to sample attrition. Survey response rates are monitored on an ongoing basis through bi-weekly CQI reports produced by the evaluation team using the nFORM Survey Completion Summary operational report and Qualtrics response data export feature. Response rates are calculated by dividing the number of participants who responded to each survey by the number of participants who were eligible to respond to that survey up to that time point. If CQI reports show that survey response rates are below intended targets, the CQI team brainstorms and implements strategies to increase response rates to minimize sample attrition caused by survey nonresponse. Reasons for survey nonresponse, to the degree that they are known, will be reported in the CONSORT diagram. Individuals with survey nonresponse at the follow-up time point will not be included in the analytic sample; the analysis for each outcome will use complete case data.

Item nonresponse

Item nonresponse can also lead to sample attrition for particular outcome measures if participants skip survey items that are aligned with the research questions for this study. Item nonresponse is calculated by dividing the number of participants who respond to a survey item by the number who were eligible and able to answer a question based on skip/display logic. As stated in the data preparation section above, respondents taking paper surveys may violate skip/display logic, and invalid responses will be dropped before item-level response rates are calculated. We will also note what proportion of the sample skipped out of the relationship and employment attitude questions to give context to the item nonresponse.

Constructed outcome measures

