All outcome measures for this study are constructed averages calculated using a number of theoretically and empirically related survey items. As mentioned in the previous section, a respondent who answers some but not all survey items in a given outcome construct will have their outcome value assigned as missing if they do not respond to at least 80% of the items in the construct. We will not impute missing baseline or outcome data for our analyses. Based on the recommendation from ACF, we will use the cautious attrition threshold from the What Works Clearinghouse (WWC) to assess whether attrition can be considered high or low.

Assessment of baseline equivalence

Per the WWC's standards, we will use effect sizes (i.e., standardized mean differences), to examine the baseline equivalence between the study groups. Effect size is defined as the difference between the intervention group mean and the comparison group mean, divided by the pooled standard deviation. We will calculate the effect size for demographic characteristics (such as gender, age, and race/ethnicity, as reported on the nFORM Applicant Characteristics Survey) and each baseline outcome of interest depending on the type of variable: Hedge's g , for continuous variables; and Cox's index, for dichotomous variables. We can determine baseline equivalence by comparing each outcome's effect size using the WWC standard, which suggests that if the corresponding effect size is 0.05 or less in absolute value, it is considered "small," and we can conclude that it satisfies baseline equivalence without statistical adjustment. However, if the effect size falls between 0.05 and 0.25, it is considered "moderate," and it will require a statistical adjustment to meet baseline equivalence (we will use statistical adjustments such as regression adjustments or matching/weighting). Lastly, in the case that the effect size is greater than 0.25, it will be considered "large", which shows that the differences at baseline are too large to meet WWC standards, even with statistical adjustments. In that case, we will apply appropriate caveats to any interpretation of the results.

Condition crossover

At the primary RCT enrollment site, Franklin CBCF, condition crossover is not possible due to restrictions put in place when designing the implementation of the two delivery formats. If a participant who was

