Next, we will conduct an analysis to see how outcome construct measures change if we use mean imputation to replace missing items in the multi-item scales used to create our outcome variables. This is the mean based on observed values from the rest of the sample for that item. The current plan is not to use any imputation for outcome measures, including constructed outcomes from multiple survey items, and instead to make the denominator for the calculation of the average score be equal to the number of non-missing items in that construct.

Finally, we plan to conduct a sensitivity analysis regarding the timing of the follow-up survey. Given changes in follow-up data collection protocol at Franklin CBCF, we anticipate that some respondents will have taken their paper follow-up survey earlier than intended. The sensitivity analysis will repeat our analyses using only people who completed their follow-up survey within the intended data collection window (5-7 months post-enrollment).

5. Analyses addressing secondary research questions

The analytic approach for answering the secondary research question about partner relationship behaviors will be the same as the approach taken for the primary research questions.

Figure A.3. CONSORT diagram for individual clients, for studies in which consent occurred before assignment

Eligible for 6-month post-enrollment follow-up (n = 206)

To be eligible, a participant must have provided consent and taken either the nFORM baseline or local evaluation baseline survey

Completed follow-up (n = 64)

Data collection: July 1, 2023-July 22, 2024

Reasons for non-completes (n = 1) (that can be accounted for)

Consent revoked (n = ___), declined survey (n = ___), deceased (n = ___), dropped out (n = 7), moved (n = ___), incarcerated (n = 1)

Eligible for 6-month post-enrollment follow-up (n = 190)

To be eligible, a participant must have provided consent and taken either the nFORM baseline or local evaluation baseline survey

Completed follow-up (n = 52)

Data collection: July 1, 2023-July 22, 2024

Reasons for non-completes (n = 1) (that can be accounted for)

Consent revoked (n = ___), declined survey (n = ___), deceased (n = ___), dropped out (n = 4), moved (n = ___), incarcerated (n = 1)

Figure A.4. Survey items linked to research questions

Measure	Item Response	Are these items linked to a primary research question?	Are these items linked to a secondary research question?
Partner relationship beliefs 8 items			No

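### The item-imputation sensitivity analysis uses a pooled item mean, which shrinks the arm difference by about the share of items filled and leaves the test almost unchanged, so it says little about robustness

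*Combined protocol and SAP*

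**What the plan says.** Section D.4 lists three sensitivity analyses: a 70% instead of an 80% item-completeness threshold, mean imputation of skipped items, and a restriction to surveys taken 5-7 months after enrollment. The second is meant to "see how outcome construct measures change if we use mean imputation to replace missing items in the multi-item scales". The filler is defined in one sentence: "This is the mean based on observed values from the rest of the sample for that item." Arm is not mentioned, so the natural reading is a mean pooled over both arms. It is a single imputation.

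The main analysis does not impute. Section D.2 says "We will not impute missing baseline or outcome data for our analyses", and D.4 confirms that the main scoring will "make the denominator for the calculation of the average score be equal to the number of non-missing items in that construct".

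Two completeness rules bear on how much would be filled. Section D.1 (Constructed outcome measures) says that "respondents who answer less than 80% of survey items associated with a constructed measure will be dropped from the analysis for that outcome". Section A.3 sets a score to missing for a respondent who is "missing more than 1 item used for creating the employment construct or more than 2 items for creating the financial construct". D.4 does not say whether either rule applies in the imputation analysis.

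**The concern.** Section D.4 exists to test whether the primary results are robust, and this is its only analysis that imputes items. A pooled item mean contains no information about the person or the arm. Putting it into both arms therefore pulls the arm means together, whatever the true effect.

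Two misreadings could follow. If the imputed estimate is smaller than the main one, a reader may take the result to be fragile when the method alone produced the drop. If significance agrees, a reader may be reassured when the method could hardly have given anything else.

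**Working it through.** **Inputs from the plan.** Employment scale 8 items and financial scale 7 items (Tables 1 and 2 in A.3, Figure A.4); target 384 per arm (C.1); 50-50 assignment (C.1). The plan gives no item-missing rate for the primary scales, so there is no figure of its own to reproduce. The 25-28% in D.1 refers to relationship items.

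**Assumptions.** Item missingness m of 5%, 10% and 20%; Cronbach's alpha 0.75 (the plan requires at least 0.60); true difference 0 or 0.20 SD; continuous items; unadjusted two-sample comparison; 1,500 to 4,000 runs per setting.

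**Step 1, the estimate.** Suppose items are skipped at rate m in both arms, unrelated to the answers. The expected value of item j in arm a after filling is (1 - m) × (arm mean) + m × (pooled mean). The pooled term cancels between arms, so the difference becomes (1 - m) × (true difference).

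**Step 2, the standard error.** For a respondent with r of k items missing, the filled score is (1 - r/k) × (own mean of answered items) + (r/k) × (mean of the fillers). The first term is the main-analysis score shrunk by 1 - r/k, and the second adds nothing about the person. Spread and difference shrink together, so z should hardly change on the same respondents.

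**Step 3, simulation within the completeness cutoff (true difference 0.20 SD).** Entries are estimate (model SE), mean z.

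| Scale, cutoff | Item missingness | Share filled among those kept | Main scoring | Pooled mean imputation | Ratio of estimates | Ratio of SEs |
|---|---|---|---|---|---|---|
| 8 items, at most 1 missing | 5% | 3.7% | 0.2011 (0.0748), 2.690 | 0.1936 (0.0720), 2.689 | 0.963 | 0.963 |
| | 10% | 5.9% | 0.1969 (0.0808), 2.439 | 0.1852 (0.0760), 2.439 | 0.941 | 0.941 |
| | 20% | 8.3% | 0.1988 (0.1032), 1.929 | 0.1825 (0.0945), 1.934 | 0.918 | 0.916 |
| 7 items, at most 2 missing | 5% | 4.9% | 0.1973 (0.0730), 2.704 | 0.1876 (0.0695), 2.703 | 0.951 | 0.952 |
| | 10% | 9.1% | 0.1992 (0.0743), 2.685 | 0.1810 (0.0675), 2.684 | 0.909 | 0.908 |
| | 20% | 15.4% | 0.1992 (0.0804), 2.479 | 0.1683 (0.0679), 2.479 | 0.845 | 0.845 |

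The ratios match 1 minus the share filled, as in step 1.

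**Step 4, all partial responders filled (8 items, against full data).** 0.1914/0.2016 = 0.949, 0.1778/0.1985 = 0.896 and 0.1603/0.2003 = 0.800 at 5%, 10% and 20%.

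A separate run with baseline adjustment and five-point items (768 in total, 8 items) gave 0.96, 0.94 and 0.92 within the cutoff and 0.95, 0.90 and 0.80 with all partial responders filled. Averaging the answered items gave 1.00.

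**Step 5, validity of the test.** With items missing at random and no true difference, pooled imputation rejected in 4.4% to 5.3% of runs. The ratio of model SE to sampling SD was 0.96 to 1.02 across the settings in steps 3 to 5, in line with the full-data runs. What fails is coverage of the unshrunken effect: with all partial responders filled at 20%, the bias is about 0.04 against an SE of 0.0601, and a nominal 95% interval covers 0.20 about 90% of the time.

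**Step 6, non-random skipping.** With low answers skipped more often, missingness of 5% in one arm and 15% in the other, and no true difference, the main scoring gave a false difference of 0.276. Pooled imputation within the cutoff gave 0.254, so the check would not have exposed the bias.

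**Step 7, how much could be filled.** One of 8 is 12.5%. For the financial scale, 20% of 7 is 1.4, so the 80% rule allows one missing item (1/7 = 14.3%). A.3 allows two (2/7 = 28.6%, leaving 5/7 = 71.4% answered, which fails the 80% rule). Since 71.4% passes the 70% threshold, the 70% sensitivity analysis would change nothing for the financial scale if A.3 governs.

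**The case against.** The strongest reply is that no primary estimate is touched. The main analysis averages answered items, which was unbiased when items were missing at random. The imputation analysis is described as a comparison of scoring rules, and it does make that comparison. Within the cutoff an employment respondent can miss only one item, and the primary items are shown to everyone, so skip logic does not create gaps in them. The 70% threshold analysis also bears on skipped items, by changing who is included. All of this stands, and it limits the size and the consequence of the point.

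Three stronger readings are tempting, and the documents do not support them:

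- *That the standard error is understated and the test too liberal.* A smaller SE than in the main analysis is not an understated one. It matches the sampling variation of the shrunken estimate, and type I error is held.
- *That the analysis cannot test robustness at all.* It compares scoring rules. If it reaches people below the cutoff, it also brings back excluded partial responders: in the step 6 setting, filling all of them cut the false difference to 0.130. The narrower criticism is that on the same respondents it says little about non-random skipping, and that any change in the estimate is mixed with shrinkage.
- *That someone who skipped a whole scale would receive an invented score.* This needs the 80% rule not to carry over, which D.4 leaves unsaid. For people with no follow-up survey the plan is clear: "Individuals with survey nonresponse at the follow-up time point will not be included in the analytic sample".

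**Conclusion.** The point holds for the sensitivity analysis only. Pooled item-mean imputation shrinks the arm difference by about the share of items filled. For the eight-item scale this is about 4-8% within the cutoff, and 5-20% if all partial responders are filled. For the seven-item scale it is about 5-15% if two missing items are allowed. These sizes rest on assumed item missingness of 5-20%, equal in both arms and unrelated to the answers, and on reading the mean as pooled over arms.

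The SE shrinks in proportion and z is almost unchanged on the same respondents. A smaller estimate would therefore be an artefact, agreement in significance is close to automatic, and the interval is centred on a shrunken effect. The change is a cheap improvement to a secondary check.

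**What to change.** In D.4, replace mean imputation with item-level multiple imputation among follow-up respondents: chained equations, at least 20 imputations, results combined by Rubin's rules. Include in the imputation model arm, the person's other follow-up items, baseline items, age, gender, race, facility and follow-up timing. Build the composite after imputation and run the same regression as in D.3.

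State which partial responders enter this analysis, in particular whether the 80% rule applies. Reconcile the A.3 allowance of two missing financial items with the 80% rule in D.1 and D.2.

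Arm-specific item means are not a safe shortcut. They remove the shrinkage but do understate the SE: type I error was 8.0% and 10.9% at 10% and 20% item missingness in the eight-item runs.

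The cost is SAP wording, a little more analysis work in standard R code, and slightly wider intervals in a sensitivity analysis. Two limits remain. Multiple imputation assumes that skipping is explained by the variables in the imputation model. It also does nothing for missing follow-up surveys, the larger gap: 64 + 52 = 116 of 206 + 190 = 396 eligible (29.3%) had completed follow-up at the July 22, 2024 data pull (Figure A.3).
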